6.2.1. Preparation and Dispensing

Within this protocol, preparation refers to the investigator site activities performed to make the study intervention ready for administration or dispensing to the participant by qualified staff. Dispensing is defined as the provision of study intervention, concomitant treatments, and accompanying information by qualified staff member(s) to a healthcare provider, participant in accordance with this protocol. Local health authority regulations or investigator site guidelines may use alternative terms for these activities.

PF-07258669 and placebo oral dosing solutions and suspensions will be prepared in the CRU by 2 operators, 1 of whom is a pharmacist. Details of dose preparation will be given in a separate EDR. Prepared doses will be provided in unit dose containers and labeled in accordance with Pfizer regulations and the investigator site's labeling requirements.

PFIZER CONFIDENTIAL

Page 34

6.3. Measures to Minimize Bias: Randomization and Blinding

6.3.1. Allocation to Study Intervention

The investigator will assign participant numbers to the participants as they are screened for the study. Pfizer will provide a randomization schedule to the investigator and, in accordance with the randomization numbers, the participant will receive the study treatment regimen assigned to the corresponding randomization number.

Participants will be randomly assigned to receive study intervention from a central randomization scheme. Investigators and participants will remain blinded to each participant's assigned study intervention throughout the course of the study. In order to maintain this blind, an otherwise uninvolved third party (for example, pharmacist) will be responsible for the preparation and dispensing of all study intervention according to the randomization schedule and assigned treatment for the individual participant.

6.3.2. Breaking the Blind

The method for breaking the blind in this study will be manual. In case of an emergency, the investigator has the sole responsibility for determining if unblinding of a participant's treatment assignment is warranted. Participant safety must always be the first consideration in making such a determination. If the investigator decides that unblinding is warranted, the investigator should make every effort to contact the sponsor prior to unblinding a participant's treatment assignment unless this could delay further management of the participant. If a participant's treatment assignment is unblinded, the sponsor must be notified within 24 hours after breaking the blind. When the blinding code is broken, the reason must be fully documented in the CRF.

Blood specimens will be obtained from all participants for PK analysis to maintain the study blind at the investigator site. Only the investigator site staff and blinded study monitor, if assigned, will be blinded to study treatment. A limited number of Pfizer study team personnel will be unblinded to participant treatments in order to permit real-time interpretation of the safety and PK data and provide information necessary to potentially alter the dose-escalation sequence. The blinded study monitor, if assigned, will remain blinded to treatment until all monitoring for the study has been completed. Specimens from participants randomized to placebo will not be routinely analyzed. To minimize the potential for bias, treatment randomization information will be kept confidential by Pfizer unblinded personnel and will not be released to the blinded investigator or blinded investigator site personnel until the study database has been locked or the investigator requests unblinding for safety reasons.

6.4. Study Intervention Compliance

When participants are dosed at the site, they will receive study intervention directly from the investigator or designee, under medical supervision. The date and time of each dose administered in the clinic will be recorded in the source documents and recorded in the CRF. The dose of study intervention and study participant identification will be confirmed at the time of dosing by a member of the study site staff.

6.5. Concomitant Therapy

Use of prescription or nonprescription drugs and dietary and herbal supplements are prohibited within 7 days or 5 half-lives (whichever is longer) prior to the first dose of study intervention through the follow-up contact. Limited use of nonprescription medications that are not believed to affect participant safety or the overall results of the study may be permitted on a case-by-case basis following approval by the sponsor. Acetaminophen/paracetamol may be used at doses of ≤ 1 g/day.

Females taking hormone replacement therapy may be eligible to participate in this study if they are willing to discontinue therapy at least 28 days prior to the first dose of study treatment and remain off hormonal therapy for the duration of the study.

All concomitant treatments taken during the study must be recorded with indication, daily dose, and start and stop dates of administration. All participants will be questioned about concomitant treatment at each clinic visit.

Treatments taken within 28 days before the first dose of study intervention will be documented as a prior treatment. Treatments taken after the first dose of study intervention will be documented as concomitant treatments.

6.5.1. Rescue Medicine

There is no rescue therapy to reverse the AEs observed with PF-07258669; standard medical supportive care must be provided to manage the AEs.

6.6. Dose Modification

The decision to proceed to the next dose level of PF-07258669 (eg, an increase, decrease, or repeat of a previous dose level) will be made by the study team and the investigator based on safety, tolerability, and preliminary PK data at the prior dose level. At least 6 participants (including at least 1 placebo participant) must complete the prior dose level. PK data through at least 24 hours post-dose will be reviewed.

The dosing schedule may also be adjusted to add cohorts (8 participants/cohort) to evaluate additional dose levels. The study procedures for these additional participant(s)/cohort(s) will be the same as that described for other study participants/cohorts.

6.6.1. Dose Escalation and Stopping Rules

Precautionary sentinel dosing will be used in each period of each cohort. Two participants (1 receiving PF-07258669 and 1 receiving placebo) within a period will be dosed initially before the remaining participants of that period are dosed. Safety and tolerability data through at least 24 hours post-dose for the sentinel participants will be reviewed prior to dosing the remaining participants of that period.
Dose escalation stopping rules will be used to determine whether the maximal tolerated dose has been attained. Dose escalation may be stopped if it is determined that the limits of safety and/or tolerability have been reached. This decision will be made after a discussion takes place between the sponsor study team and the investigator. The sponsor study team may not overrule the investigator's decision to stop dose escalation. If dose escalation is stopped because of any of these criteria, additional cohorts may receive the same or lower doses of the study intervention.

The dose escalation will be terminated based on the following criteria:

- If 50% or more of the participants receiving active drug at a given dose level (but not participants receiving placebo) develop similar clinically significant laboratory, ECG, or vital sign abnormalities, in the same organ class, indicating dose-limiting intolerance.
- Severe nonserious AEs, considered as, at least, possibly related to study intervention administration, in 2 participants at a given dose level (but not participants receiving placebo), independent of within or not within the same system organ class, indicating dose-limiting intolerance.
- Dosing will be paused for any SAE that occurs in a participant receiving active treatment until causality is fully assessed by the PI and sponsor. Dosing may resume if the SAE is determined to be not drug-related by the PI and sponsor. If the SAE is determined to be either drug-related or unknown, either dosing will cease or the SAE will be evaluated by the sponsor's protocol review committee (or similar review group), which is independent of the study team and investigators. If the protocol review committee determines that dosing may resume, a plan that mitigates risks to participants with the resumption of dosing will be implemented. Such a plan could include a revision of inclusion/exclusion criteria, repeating or reducing the dose, or adding appropriate safety monitoring.
- It is determined that the limit of safety and/or tolerability has been reached. This decision will be made following discussions between the study team and the investigator.
- Other findings that, at the discretion of the study team and investigator, indicate that dose escalation should be halted.

• If, based on the observed data, the group mean C_{max} or AUC (based on total plasma concentration) of the next planned dose is projected to exceed the escalation limits, that dose will not be explored. Modified doses may be explored if they are not expected to exceed PK stopping criteria.

PFIZER CONFIDENTIAL

Progression to the next dose level will occur if the last dose was well tolerated and after satisfactory review of the available safety and PK data.

At a minimum, review of safety and tolerability data through 48 hours post-dose, and PK data through 24 hours post-dose, is required in order to escalate to the next dose level. The safety and tolerability assessments are outlined in the study endpoints and include assessment of adverse events, clinical safety laboratory tests, vital signs, continuous cardiac monitoring, 12-lead electrocardiograms, respiratory rate, oral body temperature, physical examinations, and neurological examinations.

6.7. Intervention After the End of the Study

No intervention will be provided to study participants at the end of the study.

7. DISCONTINUATION OF STUDY INTERVENTION AND PARTICIPANT DISCONTINUATION/WITHDRAWAL

7.1. Discontinuation of Study Intervention

In rare instances, it may be necessary for a participant to permanently discontinue study intervention (definitive discontinuation). Reasons for definitive discontinuation of study intervention include the following: adverse event, or some other (administrative) reason.

If study intervention is definitively discontinued, the participant will not remain in the study for further evaluation. See the SoA for data to be collected at the time of discontinuation of study intervention.

In the event of discontinuation of study intervention, it must be documented on the appropriate CRF/in the medical records whether the participant is discontinuing further receipt of study intervention or also from study procedures, posttreatment study follow-up, and/or future collection of additional information.

ECG Changes

A participant who meets either of the following bulleted criteria based on the average of triplicate ECG readings will be withdrawn from the study intervention.

- QTcF > 500 msec.
- Change from baseline: QTcF >60 msec.

If a clinically significant finding is identified (including, but not limited to, changes from baseline in QTcF after enrollment), the investigator or qualified designee will determine if the participant can continue in the study and if any change in participant management is needed. This review of the ECG printed at the time of collection must be documented. Any new clinically relevant finding should be reported as an AE.

Potential Cases of Acute Kidney Injury

Abnormal values in SCr concurrent with presence or absence of increase in BUN that meet the criteria below, in the absence of other causes of kidney injury, are considered potential cases of acute kidney injury and should be considered important medical events.

An increase of $\geq 0.3 \text{ mg/dL}$ (or $\geq 26.5 \mu \text{mol/L}$) in SCr level relative to the participant's own baseline measurement should trigger another assessment of SCr as soon as practically feasible, preferably within 48 hours from awareness.

If the second assessment (after the first observations of $\ge 0.3 \text{ mg/dL}$ [or $\ge 26.5 \text{ }\mu\text{mol/L}$] in SCr relative to the participant's own baseline measurement) is $\ge 0.4 \text{ mg/dL}$ (or $\ge 35.4 \text{ }\mu\text{mol/L}$), the participant should be discontinued from the study and adequate, immediate, supportive measures taken to correct apparent acute kidney injury.

Participants should return to the investigator site and be evaluated as soon as possible, preferably within 48 hours from awareness of the second assessment confirming abnormal SCr result. This evaluation should include laboratory tests, detailed history, and physical assessment. In addition to repeating SCr, laboratory tests should include serum BUN, serum creatine kinase, and serum electrolytes (including at a minimum potassium, sodium, phosphate/phosphorus, and calcium), in addition to urinary dipstick, urine microscopic examination, and urinary indices. All cases confirmed on repeat testing as meeting the laboratory criteria for acute kidney injury, with no other cause(s) of laboratory abnormalities identified, should be considered potential cases of drug-induced kidney injury irrespective of availability of all the results of the investigations performed to determine etiology of the abnormal SCr. If \geq 2 healthy participants in a given period are noted to have 2 consecutive SCr results of \geq 0.3 mg/dL (or \geq 26.5 µmol/L), an assessment of whether the finding may be considered an adverse drug reaction should be undertaken.

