Visit Identifier ^a	Screening		Period 1 to Period 4 ^b Follow-Up ET								ET/DC									
	Day -28	Day						Day	1						D	ay	Day	Visit:	Contact:	
	to Day -2	-1						-								2	3	Day	28-35	
Hours After Dose			0 ^d	0.17	0.5	1	1.5	2	4	6	8	10	12	16	24	36	48	8±2°	Days ^c	
Serum FSH ^r	Х																			
HBcAb, HBsAg, HBsAb, HCVAb, HIV testing	Х																			
Pfizer Prep B2 banked sample ^s			Х																	
Pfizer Prep D1.5 banked sample ^s			Х																	
PF-07258669 plasma pharmacokinetics			Х	Х	Х	Х	Х	Х	Х	Х	Х		Х	Х	Х	Х	Х			Х
CCI																				
Urine Samples for:																				
Urine drug test	Х	Х																		
Clinical safety laboratory tests ^q	Х	Х													Х		Х	Х		Х
Abbreviations: \rightarrow = ongoing/continuous event; AE = adverse event; BP = blood pressure; CRU = clinical research unit; DC = discontinuation; ECG = electrocardiogram;																				
ET = early termination; FSH = follicle stimulating hormone; HBcAb = hepatitis B core antibody; HBsAb = hepatitis B antibody; HBsAg = hepatitis B surface antigen;																				
HCVAb = hepatitis C antibody: HIV = human immunodeficiency virus: PR = pulse rate.																				

a. Day relative to start of study treatment (Day 1).

b. There will be a washout interval of ≥ 7 days between doses within an individual participant.

- c. Onsite follow-up visit to occur on Day 8 ±2 days in Period 4 only. Follow-up contact may occur via telephone contact and must occur 28-35 days after administration of the final dose of study intervention.
- d. Day 1 activities at time=0 hours are prior to the dose, except for study treatment administration.
- e. Participants may be confined to the CRU after completion of Day 3 activities at the discretion of the investigator or if safety, tolerability, or PK data dictate the need to prolong confinement in the CRU.
- f. Period 1 only. Review any changes from Screening.
- g. Contraception only required for male study participants and is recommended for partners of male study participants who are WOCBP.
- h. COVID-19 questionnaire includes check for suspected contact, risk zone, and COVID-19 related symptoms.
- i. Testing for active COVID-19 infection via testing for SARS-CoV-2 viral dosing (using PCR). To meet PCRU practice, testing for active COVID-19 infection will be performed at screening, admission, and follow-up visit.

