7.2. Participant Discontinuation/Withdrawal From the Study

A participant may withdraw from the study at any time at his/her own request. Reasons for discontinuation from the study include the following:

- Refused further follow-up;
- Lost to follow-up;
- Death;
- Study terminated by sponsor;
- Discretion of the investigator or sponsor for safety or behavioral reasons, or the inability of the participant to comply with the protocol required schedule of study visits or procedures.

At the time of discontinuing from the study, if possible, an early discontinuation visit should be conducted. See the SoA for assessments to be collected at the time of study discontinuation and follow-up and for any further evaluations that need to be completed.

The early discontinuation visit applies only to participants who are enrolled/randomized and received at least 1 dose of the study intervention and then are prematurely withdrawn from the study. Participants should be questioned regarding their reason for withdrawal.

The participant will be permanently discontinued both from the study intervention and from the study at that time.

If a participant withdraws from the study, he/she may request destruction of any remaining samples taken and not tested, and the investigator must document any such requests in the site study records and notify the sponsor accordingly.

If the participant withdraws from the study and also withdraws consent (see Section 7.2.1) for disclosure of future information, no further evaluations should be performed and no additional data should be collected. The sponsor may retain and continue to use any data collected before such withdrawal of consent.

Lack of completion of all or any of the withdrawal/early termination procedures will not be viewed as protocol deviations so long as the participant's safety was preserved.

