8.3.1. Time Period and Frequency for Collecting AE and SAE Information

The time period for actively eliciting and collecting AEs and SAEs ("active collection period") for each participant begins from the time the participant provides informed consent, which is obtained before the participant's participation in the study (ie, before undergoing any study-related procedure and/or receiving study intervention), through and including a minimum of 28 calendar days, except as indicated below, after the last administration of the study intervention.

Follow-up by the investigator continues throughout and after the active collection period and until the AE or SAE or its sequelae resolve or stabilize at a level acceptable to the investigator and Pfizer concurs with that assessment.

For participants who are screen failures, the active collection period ends when screen failure status is determined.

If the participant withdraws from the study and also withdraws consent for the collection of future information, the active collection period ends when consent is withdrawn.

If a participant definitively discontinues or temporarily discontinues study intervention because of an AE or SAE, the AE or SAE must be recorded on the CRF and the SAE reported using the CT SAE Report Form.

Investigators are not obligated to actively seek AE or SAE after the participant has concluded study participation. However, if the investigator learns of any SAE, including a death, at any time after a participant has completed the study, and he/she considers the event to be reasonably related to the study intervention, the investigator must promptly report the SAE to Pfizer using the CT SAE Report Form.

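### Protocol 7.1 removes a participant taken off study drug from further evaluation, which conflicts with the 28-day adverse event collection and the 28-35 day contact required elsewhere

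*Protocol*

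**What the plan says.** On definitive discontinuation, Protocol 7.1 says: "If study intervention is definitively discontinued, the participant will not remain in the study for further evaluation". It lists an adverse event first among the reasons. Its pointer to the schedule covers one moment only: "See the SoA for data to be collected at the time of discontinuation of study intervention". The next paragraph requires a record of "whether the participant is discontinuing further receipt of study intervention or also from study procedures, posttreatment study follow-up, and/or future collection of additional information".

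Other sections bear on the same participant:

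- **8.3.1** sets active AE/SAE collection for each participant from consent "through and including a minimum of 28 calendar days, except as indicated below, after the last administration of the study intervention". The early ends it lists are screen failure and the case where a participant "withdraws from the study and also withdraws consent for the collection of future information, the active collection period ends when consent is withdrawn".
- **1.3, footnote c:** "Follow-up contact may occur via telephone contact and must occur 28-35 days after administration of the final dose of study intervention".
- **7.2.1** says that participants who themselves ask to stop drug stay in the study and must be followed, unless they specifically withdraw consent for further contact.
- **7.2** refers participants leaving the study to the SoA "for assessments to be collected at the time of study discontinuation and follow-up and for any further evaluations that need to be completed", but also says: "The participant will be permanently discontinued both from the study intervention and from the study at that time".
- **8.3.1**, near its end, releases investigators from actively seeking events once a participant's study participation has concluded.

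**The concern.** Safety and tolerability form the primary objective of this first-in-human study. For a participant taken off drug, the contact 28-35 days after the last dose is the last scheduled check for adverse events. The on-site Day 8 visit belongs to Period 4 only, so someone stopped in Periods 1 to 3 has no other scheduled check after the ET/DC visit.

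Section 7.1 is where a site will look when it stops drug. Taken at its word, it ends evaluation there. The effect would also be uneven. A participant who chooses to stop is expressly followed under 7.2.1, while one removed by the investigator or sponsor for an adverse event falls under the 7.1 sentence. The second participant matters more for safety. The SoA also schedules the contraception check at that contact, so it would be lost too.

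**Working it through.** There is no figure in the plan to reproduce, and no formal hypothesis test depends on this point. The check is to apply the texts to one case: a participant dosed in Period 2 whom the investigator removes from study drug because of an adverse event, without any withdrawal of consent.

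1. **7.1, disputed sentence.** The participant does not stay for further evaluation. The SoA pointer leads to the ET/DC column only.
2. **7.1, record-keeping paragraph.** The site must document whether the participant stops drug only or also stops post-treatment follow-up. That distinction has little meaning if everyone who stops drug leaves the study.
3. **7.1, kidney-injury rule.** A participant discontinued from the study for a confirmed creatinine rise is asked to return for laboratory tests, history and physical assessment. Here too 7.1 expects evaluation after discontinuation.
4. **8.3.1, collection period.** At least 28 days after the last dose. After dosing, the listed early end needs withdrawal from the study and also withdrawal of consent. Stopping drug is not listed. The same section mentions definitive discontinuation because of an adverse event, requires the event to be recorded, and does not shorten the window.
5. **SoA footnote c.** The contact is mandatory, with no exemption for discontinued participants.
6. **7.2.1.** States the rule one would want, but for participants who request to stop. It does not cover this case in terms.
7. **7.2 and the closing part of 8.3.1.** If 7.1 is taken to end participation, 7.2 dates the end to that moment, and 8.3.1 then removes the duty to seek events actively.

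Items 2 to 5 support continued collection, and item 6 supports it by analogy. Items 1 and 7 form a coherent route to stopping at the ET/DC visit. The first group is stronger, because 8.3.1 and footnote c are the specific rules on collection and contact, and both are mandatory.

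**Time at stake.** On the combined reading, no days of the 28-day minimum are lost. If a site lets 7.1 prevail, the shortfall against that minimum is 28 − d days, where d is the number of days from last dose to the ET/DC visit. The documents give no value for d: the ET/DC column carries no day, and the washout is at least 7 days with no upper limit. The shortfall therefore cannot be fixed. What can be stated is the unit: one scheduled contact per discontinued participant.

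**The case against.** The strongest reply is that the matter is already handled. The section dedicated to adverse event collection governs, footnote c is mandatory, and the 7.1 sentence mentions neither AE collection nor the 28-35 day contact. It can be read as meaning no further dosing periods. Section 7.2.1 settles participant-initiated stops, which narrows the gap to stops by the investigator or sponsor. Known events are followed until they resolve or stabilize (8.3.1, 8.3.3), clinically significant laboratory abnormalities are repeated (8.2.7), and prolonged QTcF has its own monitoring rules (8.2.6).

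Most of this stands, and it is why the point is minor. It does not remove the conflict: the milder meaning has to be supplied by the reader, and 7.2 and the end of 8.3.1 can be cited against it.

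A reader might infer more than the documents support:

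- **That the protocol ends safety follow-up for everyone who stops drug.** It does not, given 7.2.1, 8.3.1 and footnote c.
- **That a stated number of days or share of participants is lost.** Neither the ET/DC day nor the number of discontinuations is given. Section 7.1 says only that such cases are rare.
- **That the end-of-study definition in 4.4 proves the contact is required.** It defines who has completed the study, so it does not settle what is owed by someone who stops early.

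**Conclusion.** The conflict is real and is in current text. The better combined reading keeps the contact, but the wording of 7.1, with support from 7.2 and 8.3.1, lets a site end follow-up at the ET/DC visit, chiefly for participants removed because of an adverse event. The consequence is minor. New or late-onset events could go unrecorded in the few participants who are taken off drug at a site that applies 7.1 literally. No calculation changes. The escalation rule in 6.6.1, which needs safety data through 48 hours and PK data through 24 hours, is untouched. The conclusion assumes nothing about discontinuation rates or visit timing. It does assume that a specific mandatory rule should prevail over a general sentence, which a site may not take for granted.

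**What to change.** Replace the sentence in 7.1 with wording such as: *The participant will receive no further doses or treatment periods, will complete the ET/DC assessments, and will remain in AE/SAE collection through the contact 28-35 days after his or her last dose, unless consent for further contact is withdrawn.* This brings 7.1 into line with 7.2.1.

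In 7.2, add only that dosed participants who leave the study without withdrawing consent still have the 28-35 day contact where possible. The provisions for refusal of follow-up, loss to follow-up and death should stay as they are, since a rule for stopping drug does not fit those cases.

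The SAP needs no change: section 3.1.1 already places the follow-up contact 28-35 days after the last dose. The cost is an amendment to a few lines and at most one contact per discontinued participant, possibly by telephone and already scheduled in the SoA.

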### **3.1.2. Clinical Safety Laboratory Tests**

Safety laboratory tests will be performed at the times specified in the Schedule of Activities in the protocol.

Baseline will be defined as the last non-missing pre-dose measurement for each period.

Any clinical laboratory abnormalities of potential clinical concern will be described. To determine if there are any clinically significant laboratory abnormalities, the haematological, clinical chemistry, urinalysis and other safety tests will be assessed against the criteria specified in the sponsor reporting standards. The assessment will take into account whether each participant's baseline test result is within or outside the laboratory reference range for the particular laboratory parameter.

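### Two of the three serum creatinine thresholds in Protocol Section 7.1 are written as absolute levels instead of rises from baseline, so a normal creatinine meets them.

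*Protocol*

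**What the plan says.** The acute kidney injury part of Protocol Section 7.1 has three SCr steps.

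1. **Repeat test.** A rise of at least 0.3 mg/dL (26.5 µmol/L) "in SCr level relative to the participant's own baseline measurement should trigger another assessment of SCr". This is explicitly a change.
2. **Discontinuation.** The condition on the second assessment reads "in SCr relative to the participant's own baseline measurement) is $\ge 0.4 \text{ mg/dL" (35.4 µmol/L). The baseline phrase stands inside a parenthesis that describes the first observation. Outside it, the second assessment is simply compared with 0.4 mg/dL. If the condition is met, "the participant should be discontinued from the study and adequate, immediate, supportive measures taken to correct apparent acute kidney injury".
3. **Two-participant signal.** If at least 2 participants in a period have 2 consecutive "SCr results of \geq 0.3 mg/dL", the team assesses whether the finding is an adverse drug reaction. Neither an increase nor a baseline is mentioned.

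No other section of the protocol or SAP restates steps 2 and 3 as changes. The same Section 7.1 does label the basis of one of its ECG limits: "Change from baseline: QTcF >60 msec".

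Section 7.1 does not say which baseline applies across the 4 periods. SAP Section 3.1.2 gives a rule for analysis: "Baseline will be defined as the last non-missing pre-dose measurement for each period".

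**The concern.** The repeat test should separate a transient or spurious rise from a confirmed one, and the two-participant rule should flag a cluster. A level of 0.3 or 0.4 mg/dL lies below what almost any healthy adult has. Followed exactly, the repeat cannot clear anyone and the cluster rule is always met.

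Under Section 7.1, a participant who stops study intervention permanently does not stay in the study for further evaluation. With about 6 participants on active drug per dose level (Section 9.2), each unnecessary removal costs safety and PK data. Section 8 also rules out protocol waivers, so a site that applies the sensible reading departs from the written rule.

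**Working it through.** **The plan's own figures.** With the usual creatinine conversion factor of 88.4 (not in the documents), 0.3 × 88.4 = 26.5 and 0.4 × 88.4 = 35.4 µmol/L. Both stated equivalents reproduce, so the units are not the problem.

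**Logic check, with b the baseline in mg/dL.** On the literal reading, a repeat that has returned fully to b still leads to discontinuation whenever b ≥ 0.4, and unchanged creatinine meets the cluster level whenever b ≥ 0.3. A repeat clears the participant only if it is below 0.4 mg/dL:

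| Baseline b | Fall below baseline needed to clear, literal reading | Discontinue at (change reading, b + 0.4) | Cluster level (change reading, b + 0.3) |
|---|---|---|---|
| 0.5 | more than 0.1 (20%) | 0.9 | 0.8 |
| 0.9 | more than 0.5 (56%) | 1.3 | 1.2 |
| 1.3 | more than 0.9 (69%) | 1.7 | 1.6 |

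Example: baseline 0.9, first result 1.2 (rise 0.3, so retest), repeat 0.9. The net change is 0.0, and the literal rule discontinues.

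**How often this would matter.** From the documents: 8 participants per period (6 active, 2 placebo; Section 1.2), and post-dose laboratory draws at 24 h and 48 h (Schedule of Activities). Assumed, because the documents give no figures: mean SCr m of 0.5 to 1.3 mg/dL, within-person CV of 5 to 10%, independent normal draws with SD = CV × m, and no drug effect.

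- *First trigger at one draw.* P = 1 − Φ(0.3 / (√2 × CV × m)). At m = 0.5 and CV 5%, this is 1 − Φ(8.49), about 0. At m = 1.3 and CV 10%, it is 1 − Φ(1.63) = 0.051.
- *Repeat meets 0.4 mg/dL as a level.* P = Φ((m − 0.4) / (CV × m)). The lowest value is at m = 0.5 and CV 10%: Φ(0.1/0.05) = Φ(2) = 0.977. Elsewhere in the range it is closer to 1.
- *Repeat meets 0.4 mg/dL as a change, given the first trigger.* Two rises measured from the same baseline have correlation 0.5. The bivariate normal gives at most 0.097, at m = 1.3 and CV 10%.
- *Cluster rule, change reading.* P(rise ≥ 0.3 at both 24 h and 48 h) is at most 0.0127 per participant. With 8 participants, P(at least 2) = 1 − (1 − p)⁸ − 8p(1 − p)⁷, which at p = 0.0127 is 0.0043.
- *Cluster rule, literal reading.* P(at least 2 of 8) = 1.000 at every setting.

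**Which baseline.** Take Period 1 pre-dose 0.9, Period 2 pre-dose 1.1 and Period 2 post-dose 1.2. The rise is 1.2 − 0.9 = 0.3 on the Period 1 baseline and 1.2 − 1.1 = 0.1 on the Period 2 baseline. The first trigger fires on one and not on the other.

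**The case against.** The strongest reply is that nobody would read the rule this way. The paragraph concerns abnormal values, discontinuation is tied to apparent kidney injury, and the follow-up visit is timed from "awareness of the second assessment confirming abnormal SCr result". A repeat back at baseline confirms nothing. The parenthesis in step 2 already drops the word increase while plainly meaning one, so the later thresholds can be read as the same shorthand. Section 8 sends safety issues to the sponsor for immediate discussion, which would probably stop a needless withdrawal. The cluster rule leads only to an assessment, and Section 6.6.1 already requires review of safety data through 48 hours before each escalation.

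The percentages also need care. They are conditional on a first trigger that is rare over most of the assumed range, and the extremes come from different settings. At m = 0.9 and CV 7.5%, the trigger probability is 0.084% per draw. Over 24 participants × 4 periods × 2 draws = 192 draws, that is 192 × 0.00084 = 0.16 false triggers in the whole study. The figure reaches about 9.9 only at the corner m = 1.3, CV 10%.

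All of this stands, and it limits the weight of the point. It does not alter what the sentences say. A discontinuation criterion should not depend on staff supplying its reference point, and context does not settle which period's baseline to use.

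**Conclusion.** The concern holds, as a minor point. Steps 2 and 3 are written as absolute levels and give the wrong action if followed exactly. The logical part needs only baselines of at least 0.4 mg/dL. The rates rest on the assumed SCr range, CV and independence: 97.7 to 100% of retested participants discontinued on the literal reading against 0 to 9.7% on a change basis, and the cluster rule met in 100% of periods against at most 0.43%. The literal reading would not discontinue every participant, because step 2 applies only after a first rise of at least 0.3 mg/dL. Sensitivity to kidney injury is kept. The unnamed baseline is a smaller, separate gap of missing detail, and the main conclusion does not depend on it.

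**What to change.** In Section 7.1, insert *an increase from baseline of* before the 0.4 mg/dL (35.4 µmol/L) threshold and before the final 0.3 mg/dL (26.5 µmol/L) threshold. State one baseline for all three steps: either the last pre-dose value of the period, which would match SAP Section 3.1.2, or the Period 1 pre-dose value. The size of the thresholds is the sponsor's choice and need not change. The cost is a few words in the next protocol amendment, with no added procedure, sample or data.
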